## **7. Possible risks and preventive measures**

### **7.1 Adverse event**

The investigators should faithfully fill in the adverse event recording form, record the time, severity, duration, measures taken and outcomes of adverse events. Explaining the criteria for the severity of adverse events, judging the relationship between adverse events and the trial drug was the 5-level classification standard (definitely related, possibly related, possibly unrelated, unrelated, and could not be determined). All adverse events should be traced until resolved properly or the patient's condition is stable.

Precautions for adverse events:

① Ultrasound-guided nerve block can visualize the puncture needle tips, effectively and greatly reduce the risk of local anesthetic poisoning and puncture injury.

② Local anesthetic poisoning: strict control the dose of drug, strict intraoperative monitoring. Once local anesthetic poisoning presents, it should be treated immediately according to the treatment procedure of local anesthetic poisoning, such as electrocardiogram monitoring, respiratory tract management, volume control, sedation and anticonvulsion, and the use of corresponding vasoactive drugs.

③ Puncture injury: Performing carefully and discreetly under visualization of ultrasound to ensure that tissue damage is minimized. Once present, surgery may intervene depending on severity.

Doctor will closely monitor your condition to ensure your health, and will truthfully tell you any changes in the course of the study and any newly identified adverse effects.

If you are harmed or have anything unexpected circumstances because of participating in this study, whether it is related to the intervention or not, your doctor will make a judgment and take medical action.

Physicians will try their best to prevent and treat possible harm as a result of this study. If an adverse event occurs during a clinical trial, a committee of medical experts will determine whether it is related to the intervention. Finally, according to the provisions of "Good Clinical Practice" in China, the sponsor will provide the cost of treatment and corresponding economic compensation for trial-related injuries.

## **7.2 Serious adverse event**

Serious adverse events are defined as an adverse event leading to one of the following consequences: death, extension of hospitalization time, disability, fatal reaction or teratogenicity. Any serious adverse events occurring during the clinical trials must be reported within 24 hours to the principal investigator of the Department of Anesthesiology of Tongji Hospital and the Ethics Committee of the Drug Clinical Research Base of Tongji Hospital.

## **7.3 Safety monitoring**

The data and safety management committee consists of anesthesiologists. The committee will conduct the interim analysis when half of the patients have been enrolled. If the interim analysis shows an extremely higher rate of death or significantly more complications in the trial group, the trial will stop.

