## **1. Research background**

According to the 2022 guidelines for perioperative care for liver surgery, implementing Enhanced Recovery After Surgery (ERAS) in liver surgery may improve postoperative outcomes. Compared with open hepatectomy, laparoscopic hepatectomy has the advantages of less postoperative hospitalization time and lower complication rates, which is recommended in well-trained teams and clinically appropriate situations. Postoperative pain after laparoscopic liver resection is composed of multiple factors, including somatic and visceral pain, which is caused by abdominal distension, laparoscopic port position and abdominal wall wounds. The peak pain of postlaparoscopic surgery mainly occurs in the first 24 hours, it is particularly significant to find an appropriate way to relieve pain.

Epidural analgesia has been the gold standard for perioperative pain control, but it is associated with longer hospitalization time and increased hospital costs and a higher incidence of urinary tract infections. Additionally, its use is limited by an increasing number of drugs that interfere with blood coagulation function. Regional anesthesia is an important component of multimodal analgesia, which can reduce the dosage of opioids after surgery, thereby reducing the occurrence of adverse reactions and it is helpful for postoperative recovery. Transversus abdominis plane block (TAPB) and Rectus sheath blocks (RSB) are widely used in abdominal surgery. TAPB blocks the sensory nerves of the anterolateral abdominal wall (T6-L1), and a Meta-analysis has shown that it is effective as epidural analgesia while having fewer episodes of hypotension. Bilateral rectus sheath blocks (RSB) was originally introduced to loosen the abdominal wall during surgery by blocking the terminal branches of the 9th, 10th and 11th intercostal nerves between the internal oblique and transversus abdominis muscles. It has now been shown to reduce opioid use and alleviate postoperative pain, but if the needle tip is too deep during RSB, it will have the risk of puncturing the abdominal organs. The limitation of both TAPB and RSB lies in their ability to provide somatic analgesia only without visceral analgesia.

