### **3.2 Random grouping**

Patients were randomly divided into two groups according to computer generate random number table: TAPB combined with RSB group (control group) and ESPB group (experimental group). Group assignment information was stored in a sealed opaque envelope and stored and distributed by a specific person.

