### **5. Sample estimation**

The sample size was calculated based on previous literature, requiring 27 patients per group to achieve a two-sided 0.05 significance level and 90% power of the test. A sample size of 60 was required to set a dropout rate of 10%.

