## **8.2 Statistical analysis**

The Shapiro Wilk test was used to determine the normality of data distribution for measurement data. Measurement data with normal distribution were expressed as mean  $\pm$  standard deviation, and measurement data with non-normal distribution were expressed as median (interquartile range, IQR). Measurement data were compared between groups by t test or Mann-Whitney U test according to whether the data were normal distribution, and VAS scores were compared by repeated measures analysis of variance. Count data were expressed as frequency (%), and compared between groups by using chi-square test or Fisher exact test. The value of P less than 0.05 was considered statistical significance.

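### The interim stopping rule in section 7.3 has no trigger for excess harm in the TAPB+RSB group, and its complications criterion, if read as P<0.05, would miss most moderate excesses in the ESPB group

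*Combined protocol and SAP*

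**What the plan says.** Timing (section 7.3): "The committee will conduct the interim analysis when half of the patients have been enrolled".

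Criterion (section 7.3): if the look shows an extreme excess of deaths or "significantly more complications in the trial group, the trial will stop". There are two limbs. The death limb has no number and no test. The complications limb uses the word *significantly* but gives no test, no alpha and no list of which complications count. There is no converse criterion for the other group, and no pooled or absolute event limit.

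Groups: section 3.2 makes TAPB+RSB the control group and ESPB the experimental group. *Trial group* is not defined; ESPB is the natural reading.

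Hazards: under section 6, step 4, both arms receive bilateral ultrasound-guided ropivacaine blocks. Section 1 says that "if the needle tip is too deep during RSB, it will have the risk of puncturing the abdominal organs". Section 7.1 lists puncture injury and local anaesthetic poisoning as foreseen risks without tying them to one arm.

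Other safety routes: section 7.1 has adverse events recorded, graded and followed up, with relatedness decided by medical experts. Section 7.2 has serious adverse events reported within 24 hours to the principal investigator and the ethics committee. Both apply to every patient. Neither states when the trial would stop.

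**The concern.** A harm rule that looks at one arm only is easiest to defend when the comparator involves no procedure. Here the comparator is itself a set of needle blocks, and the one hazard that the background ties to a particular study block belongs to that comparator. If the committee follows section 7.3 literally, a clear excess of puncture injuries among control patients does not meet the criterion.

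The second issue is how much the rule can detect in the arm it does cover. The look comes at half of a small trial. If the committee takes *significantly* in the sense of section 8.2, a complication rate in the ESPB group two or three times that of the control group would usually leave the rule untriggered, and a reader could mistake that silence for evidence of safety.

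**Working it through.** **Step 1. Size of the interim look.** Section 5 gives the base number: "requiring 27 patients per group to achieve a two-sided 0.05 significance level and 90% power of the test". Allowing for 10% dropout, 27 / (1 − 0.10) = 30 per group, so 2 × 30 = 60, which reproduces the stated total. Half of 60 is 30 patients, or about 15 per arm. The even split is an assumption: 27 per group implies 1:1 allocation, but no ratio or blocking is stated.

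**Step 2. Meaning of *significantly*.** Section 7.3 does not say. The only definition in the document is in section 8.2: "The value of P less than 0.05 was considered statistical significance", with chi-square or Fisher exact tests for counts. I use these as an inference.

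**Step 3. Counts needed.** Smallest number of ESPB patients with a complication, out of 15, that gives P<0.05:

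| Control events | Two-sided Fisher | Uncorrected chi-square |
|---|---|---|
| 0 | 5 | 4 |
| 1 | 7 | 6 |
| 2 | 9 | 7 |
| 3 | 10 | 9 |

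Check of the first row. Fisher, 5 vs 0: P = 2 × C(15,5) / C(30,5) = 2 × 3003 / 142506 = 0.042. Chi-square, 4 vs 0: 30 × (4 × 15)² / (4 × 26 × 15 × 15) = 108000 / 23400 = 4.62, P = 0.03.

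**Step 4. Chance of triggering.** The documents give no complication rates, so all rates below are assumed. With a control events and b ESPB events,

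chance = Σ Bin(a; 15, p_control) × Bin(b; 15, p_ESPB), summed over pairs with b > a and P<0.05.

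| Control vs ESPB rate | Two-sided Fisher | One-sided Fisher | Chi-square, uncorrected | Chi-square, corrected |
|---|---|---|---|---|
| 10% vs 20% | 4.0% | 9.5% | 9.8% | 1.9% |
| 10% vs 30% | 14.9% | 25.6% | 27.7% | 10.7% |
| 20% vs 40% | 11.1% | 19.1% | 23.2% | 10.5% |
| 10% vs 40% | 32.5% | 46.3% | 51.0% | 28.7% |
| 10% vs 60% | 73.9% | 84.5% | 87.7% | 73.4% |

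For an 80% chance by two-sided Fisher, the ESPB rate would have to be about 41% with a control rate of 0, 64% with 10%, or 76% with 20%.

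**Step 5. The other direction.** An excess in the TAPB+RSB group lies outside the criterion, so its chance of meeting the rule as written is zero at any size. This follows from the wording, not from a calculation.

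**Step 6. The death limb.** No calculation applies, because the text asks for an extreme difference and not a significant one.

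**The case against.** Four points on the other side deserve weight.

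- **Other safeguards exist.** A reader might infer that section 7.3 is the only formal protection, or that control-arm harm could never lead to a stop. The documents do not support this. Sections 7.1 and 7.2 cover both arms, and the ethics committee hears of every serious event. What stands is narrower: those sections attach no stopping consequence and no comparison by arm, so section 7.3 is the only stated stopping criterion.
- **Deaths need no P value.** A reader might infer that an excess of deaths must also reach significance. It need not: the word qualifies complications only, and a committee could call a handful of deaths against none an extreme difference. The power figures therefore apply to complications alone.
- **The word may be loose, and the test is open.** *Significantly* may be no more technical than the adverb beside it in the death limb, and section 8.2 allows either test. Two-sided Fisher gives figures well below uncorrected chi-square, which is why both are shown. If the word is loose, the low-power argument falls, but the rule then has no threshold on either limb.
- **Watching the new technique is a recognisable choice.** Section 1 describes TAPB and RSB as widely used, and section 7.1 relies on ultrasound guidance to limit puncture injury. That explains the emphasis on ESPB. It does not explain leaving out the control group when the hazard is named in the plan and covering it costs almost nothing.

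**Conclusion.** The one-directional wording is a real gap, and it rests on the text alone, given that *trial group* means ESPB: a control-arm excess of any size meets no stopping criterion in section 7.3.

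The low-power finding is conditional. It assumes P<0.05 by a section 8.2 test, 15 patients per arm and assumed event rates. Under these, a doubling from 10% or 20% triggers the rule about 4% to 11% of the time by two-sided Fisher and 10% to 23% by uncorrected chi-square.

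It would be too strong to say that harm from ESPB rarely stops the trial. At 10% vs 40% the chance is about one in three by Fisher and one in two by chi-square, and at 10% vs 60% it is 74% to 88%. Detection would be lower if some of the 30 enrolled patients had not completed follow-up at the look. None of this biases the primary comparison; it concerns oversight.

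**What to change.** Make two changes in section 7.3.

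1. Replace *in the trial group* with *in either group*.
2. State how the decision is made, for example: *At the interim look the committee will decide whether the trial should stop from the counts, by group, of deaths and block-related complications, including puncture injury and local anaesthetic poisoning. A P value may be shown as supporting information and is not a condition for stopping.*

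The second change must keep the decision to stop in the text. Deleting the significance wording and leaving only a promise to review would remove the sole complications criterion and put nothing in its place.

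Cost: no extra patients and no extra look. There is a slightly higher chance of an unneeded pause, because the decision no longer waits for significance. Someone must supply by-arm counts to the committee without unblinding the staff named in section 3.3, but the existing rule already needs a comparison by group.

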# **8.Data collection and statistical analysis**

## **8.1 Data collection**

Main observation indicator: consumption of morphine within 24 hours after surgery

Secondary observation indicators

- 1) Morphine consumption at 1h, 2h, 4h and 8h after surgery

- 2) Number of rescue analgesia at 1h, 2h, 4h, 8h and 24 hours after surgery
- 3) VAS scores in resting and coughing at 1h, 2h, 4h, 8h and 24h after surgery
- 4) CVP values at 5, 10, 15 and 30min after nerve block
- 5) QoR-15 patient questionnaire scores before and 24h after surgery
- 6) Postoperative liver function (the percentage increase of AST and ALT compare with preoperative), postoperative complications and discharge time

## **8.2 Statistical analysis**

The Shapiro Wilk test was used to determine the normality of data distribution for measurement data. Measurement data with normal distribution were expressed as mean  $\pm$  standard deviation, and measurement data with non-normal distribution were expressed as median (interquartile range, IQR). Measurement data were compared between groups by t test or Mann-Whitney U test according to whether the data were normal distribution, and VAS scores were compared by repeated measures analysis of variance. Count data were expressed as frequency (%), and compared between groups by using chi-square test or Fisher exact test. The value of P less than 0.05 was considered statistical significance.

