### **6. Research process**

The experiment was carried out in Tongji Hospital, Tongji Medical College, Huazhong University of Science and Technology. For patient who were going to undergo laparoscopic partial hepatectomy, anesthesiologists went to the ward one day before surgery for preoperative evaluation, signed the informed consent form, and screened the subjects according to the inclusion and exclusion criteria. In according with the random results, the patients were randomly divided into ESPB group (experimental group) and TAPB&RSB group (control group). The patients were instructed to use analgesic pump and visual analogue scale (VAS). (Visual analogue scale (VAS): a 100 mm transverse line with 0mm at one end of the line indicates no pain, 100mm at the other end indicates severe pain and the middle part shows different levels of pain.)

1) All patients were routinely fasted before surgery, and no preoperative medication was given.

2) After entering the operation room, the patients in the experimental group and the control group took the sitting position, and the VAS scores of the patients in the resting state and the cough state were recorded. The subjects were scored preoperatively using the QoR-15 patient questionnaire (see supplementary).

3) Electrocardiogram, blood pressure, pulse, and blood oxygen saturation were monitored. After local anesthesia, ultrasound-guided internal jugular vein catheterization was performed, which could monitor central venous pressure (CVP) and record preoperative CVP after connecting the transducer.

4) The experimental group received ultrasound-guided ESPB, and bilateral ESPB was performed at T7 segment with 20ml 0.375% ropivacaine on each side. While the control group receives ultrasound-guided TAPB combined with RSB, which was performed under the costal margin with 10ml 0.375% ropivacaine for bilateral TAPB and 10ml 0.375% ropivacaine for bilateral RSB.

5) Anesthesia was induced with methylprednisolone 5mg, dexamethasone 5mg, penehyclidine hydrochloride 0.5 mg and palonosetron 0.25 mg, sufentanil  $0.5\mu\text{g}\cdot\text{kg}^{-1}$ , etomidate  $0.15\text{-}0.20\text{ mg}\cdot\text{kg}^{-1}$  and cisatracurium  $0.20\text{mg}\cdot\text{kg}^{-1}$ .

6) Tracheal intubation was performed after 5 minutes of mask oxygen inhalation; Ultrasound guided radial artery puncture catheterization was performed to monitor ambulatory blood pressure.

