7) Maintenance of anesthesia should use 1-2% sevoflurane inhalation, dexmedetomidine  $0.5\mu\text{g}\cdot\text{kg}^{-1}\cdot\text{min}^{-1}$  and fentanyl  $0.1\text{-}0.2\mu\text{g}\cdot\text{kg}^{-1}\cdot\text{min}^{-1}$ , and maintain blood pressure at baseline values of plus or minus 20%. In volume controlled ventilation mode, tidal volume was 6ml/kg, airway pressure was maintained within 25cmH2O, and end-tidal CO2 is maintained 35-45 mmHg. CVP values were recorded at 5, 10, 15, and 30min after nerve block. ECG, HR, BP, SpO2, CVP, PetCO2, BIS value, temperature, liquid intake and output are monitored during operation. Arterial blood gas analysis was used to correct acid-base imbalance and electrolyte imbalance.

8) Analgesic coherence: 30 minutes before the end of surgery, sufentanil 5ug was injected intravenously.

9) The patient was sent to PACU for observation for one hour after awake extubation, and then connected to an analgesic pump: sufentanil 15ug, nojan 15mg, palonosetron 0.3mg, 0.9% normal saline added to 150ml. The background infusion

rate was set according to the weight <50 kg at 1ml/h, 1.5ml/h for 50-60 kg and >70 kg at 2ml/h with a single compression dose of 2ml and a lockout time of 10min. According to the needs of patients, the analgesic pump could be pressed by themselves for analgesia. If pain cannot relieve (VAS>4 at rest), the remedial analgesia with a single dose of 2mg oxycodone can be used. At 1 hour after the end of surgery, recording the VAS scores of patients in resting and coughing states and the dose of analgesic pump. Asking patients if they had any adverse reactions, such as nausea, vomiting, pruritus, dizziness, headache, respiratory depression, etc.

10) After returning to the ward, patients could press the analgesic pump by themselves for additional analgesia. Lack of pain relief (VAS> 4 points) or, at the patient's request, rescue analgesia with a single dose of diclofenac sodium suppository. The dosage of analgesic pump, times of rescue analgesia, VAS scores in the resting and coughing and adverse reactions were recorded at 2h, 4h, 8h and 24h after operation. The QoR-15 patient questionnaire was used to evaluate the postoperative recovery at 24 hours after surgery.

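### Section 8.2 adjusts no secondary outcome for its pre-operative value, although those values are collected; the two-group tests stay valid, and the only loss is precision, of unknown size

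*Combined protocol and SAP*

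**What the plan says.** Section 8.2 holds the whole analysis plan. For continuous outcomes, "Measurement data were compared between groups by t test or Mann-Whitney U test according to whether the data were normal distribution". VAS is compared by repeated-measures ANOVA and count data by chi-square or Fisher tests. No covariate or adjusted model is named.

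The pre-operative values exist:

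- **VAS** (section 6, step 2): "the VAS scores of the patients in the resting state and the cough state were recorded", on entering the operating room.
- **QoR-15** (section 6, step 2): "The subjects were scored preoperatively using the QoR-15 patient questionnaire".
- **CVP** (section 6, step 3): the instruction is to "record preoperative CVP after connecting the transducer". The block follows in step 4, so all three are measured before treatment.
- **AST and ALT** (section 8.1): the outcome is the percentage increase over the pre-operative value, so that value has to be available.

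Section 8.1 lists "VAS scores in resting and coughing at 1h, 2h, 4h, 8h and 24h after surgery" and CVP at 5 to 30 minutes after the block; it does not list their pre-block values as outcomes. QoR-15 is listed before surgery and at 24 h, but section 8.2 does not say whether the 24 h score or the change is compared.

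Section 5 gives the size of the trial: "requiring 27 patients per group to achieve a two-sided 0.05 significance level and 90% power of the test", raised to 60 in total for 10% dropout.

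**The concern.** A patient's pre-operative QoR-15, CVP or transaminase level may predict the later value of the same measure. If it does, an unadjusted comparison leaves that predictable variation in the error term. In a trial of 54 to 60 patients, the secondary treatment effects would then be estimated less precisely than the collected data allow.

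For AST and ALT the baseline is used, but only as a divisor. That fixes its coefficient at 1 on the log scale instead of letting the data estimate it.

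There is also an open choice. Baselines collected without a stated role in the analysis can be brought in, or left out, after the results are known. Naming them in advance closes that choice.

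**Working it through.** **1. The plan's own figure.** 2 × 27 = 54, and 54 / 0.90 = 60, which matches section 5. The 27 per group cannot be rebuilt, because section 5 states no difference and no SD.

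**2. Are the planned two-group tests valid without covariates?** The planned procedure (Shapiro-Wilk, then t test or Mann-Whitney) was simulated with no group difference, 27 per group and 8,000 runs per outcome shape. The rejection rate was 4.8% for normal data, 4.8% for lognormal data and 5.0% for pump-like data. This covers the omission of covariates in two-group tests. It says nothing about the assumptions of the repeated-measures model or about the interim look.

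**3. Effect of adjusting one normally distributed outcome for its baseline.** The inputs are 27 per group (section 5) and a correlation ρ between baseline and outcome. The documents do not give ρ; it is assumed to be 0 to 0.5.

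- Ideal variance ratio: 1 − ρ²
- Expected penalty for estimating the slope: 1 + 1/50 = 1.02
- Residual degrees of freedom: 52 unadjusted, 51 adjusted
- CI width ratio = √[(1 − ρ²) × 1.02] × t(51)/t(52), with t(51)/t(52) = 2.0076/2.0066

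| Assumed ρ | 1 − ρ² | × 1.02 | CI width ratio |
|---|---|---|---|
| 0 | 1.00 | 1.02 | 1.010 |
| 0.2 | 0.96 | 0.98 | 0.990 |
| 0.3 | 0.91 | 0.93 | 0.964 |
| 0.5 | 0.75 | 0.77 | 0.875 |

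Break-even is at R² of about 0.02, or ρ of about 0.14. Below that, adjustment widens the interval by at most 1%.

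**4. AST and ALT.** Percentage increase is a monotone function of log(post/pre), so a Mann-Whitney test gives the same result on either. Let s be the ratio of the post-operative to the pre-operative SD on the log scale. Then

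variance(ANCOVA) / variance(log ratio) = (1 − ρ²)s² / (1 + s² − 2ρs).

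| s (assumed) | ρ = 0.2 | ρ = 0.3 | ρ = 0.5 |
|---|---|---|---|
| 1 | 0.60 | 0.65 | 0.75 |
| 1.5 | 0.82 | 0.87 | 0.96 |
| 2 | 0.91 | 0.96 | 1.00 |

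The variance of the log ratio minus that of ANCOVA is proportional to (1 + s² − 2ρs) − (1 − ρ²)s² = (1 − ρs)², which is never negative. Before the slope penalty of about 2%, log-scale ANCOVA therefore cannot be less precise than the log ratio, whatever ρ and s are.

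The scale matters. In a lognormal simulation (27 per group, 1,500 runs, pre-operative log SD 0.4, ρ = 0.3), ANCOVA on the raw scale beat Mann-Whitney on percentage increase at s = 1 (power 0.76 against 0.61). It lost at s = 2 (0.68 against 0.79). Log-scale ANCOVA did not lose.

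**5. VAS.** The documents give no pre-operative VAS values. If most patients score near 0 mm before surgery, the baseline hardly varies and little or no gain can be expected.

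**The case against.** **This is preference, not error.** No passage is contradicted, no error rate is affected, and section 3.2 names no stratification factor that the analysis would have to reflect. That stands, and it is why the point is an optional improvement. Section 8.2 also plans P values and no confidence intervals, so the width ratios only measure precision. They apply to a single normally distributed outcome and do not carry over to Mann-Whitney or to the VAS model. Nor does silence in section 8.2 prove that the pre-block VAS and CVP will go unused: describing the groups at baseline is an ordinary use.

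**A reader might infer that the planned tests are invalid.** The documents do not support this. Patients are randomised, and the simulation shows no inflation from leaving covariates out.

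**A reader might infer that the primary outcome should be adjusted for body weight**, because the background "rate was set according to the weight <50 kg at 1ml/h, 1.5ml/h for 50-60 kg and >70 kg at 2ml/h". The link is real: the printed rates give 24, 36 or 48 mL over a full 24 h, or slightly less if the pump starts only after the hour in PACU. It does not justify the recommendation, for three reasons.

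- Weight is not a baseline of 24 h consumption, and its share of the variance is unknown. Under assumed weight distributions, with demand unrelated to weight, it explains about 15–35%, 4–14%, 2–7% and 0.8–2.6% of pump volume at demand SDs of 10, 20, 30 and 50 mL. Break-even falls at a demand SD of about 30–56 mL. If demand falls with weight (correlation −0.3), the share is 0–2.5% at demand SDs of 20–30 mL.
- These figures leave out rescue ("the remedial analgesia with a single dose of 2mg oxycodone can be used"), and no conversion to morphine is given. Rescue opioid unrelated to weight would lower them.
- A useless covariate costs only about 0.6 points of power (90.0% to 89.4%) when data are normal. If consumption is lognormal (an assumption; section 8.2 does provide for non-normal data), raw-scale ANCOVA with a useless covariate had power of about 0.84, 0.80 and 0.72 at log SDs of 0.6, 0.8 and 1.0. The planned procedure had 0.88–0.90. The loss is roughly 4 to 17 points.

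Separately, section 6 prints no background rate between 60 and 70 kg. The sponsor must reconcile that text; it is not part of this point.

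**Conclusion.** The point holds for the secondary outcomes only, as a minor and essentially free improvement. Section 8.2 names no covariate, while a matching pre-operative value is available for QoR-15, CVP, VAS, AST and ALT. The loss is precision, and the documents do not allow it to be sized. Under the assumed correlations of 0.2 to 0.5, the interval for a single normal outcome would be 1% to 12% narrower with adjustment. For AST and ALT the variance would be 0.60 to 1.00 of the log ratio's before the 2% penalty, given ρ of 0.2 to 0.5 and s of 1 to 2.

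The case is strongest for AST and ALT, where the direction does not depend on the assumed inputs apart from the slope penalty. For QoR-15 and CVP it depends on ρ exceeding about 0.14. For VAS the gain may be nil. No change to the primary analysis follows.

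**What to change.** Add to section 8.2, before unblinding:

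- **QoR-15:** compare the 24 h score by ANCOVA with the pre-operative score as covariate.
- **CVP:** include the pre-block value as covariate in the post-block comparison.
- **AST and ALT:** analyse the log post-operative value with the log pre-operative value as covariate, in place of the percentage increase.
- **VAS (optional):** add the pre-operative score to the repeated-measures model, expecting little gain if baseline pain is near 0.

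Report each adjusted difference with a 95% confidence interval. Do not add body weight to the primary analysis on the strength of this point.

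The cost is SAP wording and one degree of freedom per model. If a covariate explains nothing, the interval for a normal outcome widens by about 1%. No patients, visits or measurements are added.

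### VAS pain scores are analysed by repeated measures ANOVA with no sphericity correction, no missing-data rule and no role for the recorded baseline; a mixed model should replace it.

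*Combined protocol and SAP*

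**What the plan says.** - **Method.** Section 8.2 gives the VAS analysis in one clause: "VAS scores were compared by repeated measures analysis of variance". It names no model terms, sphericity test or correction, covariate or treatment of missing readings, and no other section does.
- **Outcome.** Section 8.1 lists as a secondary indicator "VAS scores in resting and coughing at 1h, 2h, 4h, 8h and 24h after surgery". That is five postoperative readings for each of two states.
- **Baseline.** In Section 6, step 2, before the block in step 4, "the VAS scores of the patients in the resting state and the cough state were recorded". Nothing in Section 8 gives these values a role. By contrast, Section 8.1 does name the preoperative value for recovery quality: "QoR-15 patient questionnaire scores before and 24h after surgery".
- **Primary outcome.** It is not VAS: "Main observation indicator: consumption of morphine within 24 hours after surgery".
- **Size.** Section 5 gives a figure "requiring 27 patients per group to achieve a two-sided 0.05 significance level and 90% power of the test", raised to 60 in total for 10% dropout.

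**The concern.** Three features of classical repeated measures ANOVA fit this outcome poorly.

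1. **Missed readings.** The classical procedure needs a complete row for each patient. One missed reading out of five removes the other four as well. The remaining comparison is then sound only if completers represent everyone randomised. That is a stronger condition than a likelihood-based mixed model needs.
2. **Sphericity.** The tests of time and group-by-time assume that differences between any two readings have the same variance. Readings an hour apart are likely to be more alike than readings 16 hours apart, and the spread of pain scores may change over the day. If so, the uncorrected group-by-time test rejects too often. That test asks whether the two block techniques differ in the time course of pain.
3. **Unused baseline.** A pre-block value in the same two states is already collected and could improve precision.

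The stated method also does not commit the trial to a between-group difference with a confidence interval, either over the 24 hours or at each time. Because the plan leaves these choices open, they could be made after the data are seen.

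**Working it through.** **1. The plan's own figure.** With 27 per group and 10% dropout, 27 / (1 - 0.10) = 30 per group, so 60 in total. This reproduces. Section 5 does not mention VAS, so the figure serves here only as a yardstick.

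**2. Patients lost to incomplete readings.** There are five readings per state (Section 8.1). The miss rate q per reading is an assumption, since the documents give none. If misses are independent, the share excluded is 1 - (1 - q)^5. If the same patients miss every reading, it is q. If no patient misses more than one, it is 5q.

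| q (assumed) | Excluded, independent | Range q to 5q | Of 60 | Complete per arm of 30 |
|---|---|---|---|---|
| 2% | 1 - 0.98^5 = 9.6% | 2-10% | 5.8 | 27.1 |
| 3% | 1 - 0.97^5 = 14.1% | 3-15% | 8.5 | 25.8 |
| 5% | 1 - 0.95^5 = 22.6% | 5-25% | 13.6 | 23.2 |

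Under independence, a 2% miss rate alone is about as large as the whole 10% dropout allowance.

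**3. Type I error.** The readings at 1, 2, 4, 8 and 24 h have four gaps: 1, 2, 4 and 16 h. Trials with no group effect were simulated with 27 patients per arm and five readings, 10,000 trials per pattern. The simulation error at a true 5% is sqrt(0.05 × 0.95 / 10,000) = 0.2 percentage points. All covariance patterns are assumptions. Epsilon equals 1 when sphericity holds.

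| Assumed pattern | Epsilon | Group-by-time, uncorrected | Group-by-time, Greenhouse-Geisser | Overall group test |
|---|---|---|---|---|
| Constant variance, correlation 0.5 | 1.00 | 5.1% | 4.7% | 5.2% |
| Correlation 0.7 per reading step | 0.69 | 6.6% | 4.3% | 5.1% |
| Correlation 0.9 per reading step | 0.58 | 7.7% | 4.8% | 5.2% |
| Correlation 0.9 per hour | 0.59 | 8.2% | 4.7% | 4.9% |
| Correlation 0.7 per step, SD 20, 18, 15, 12, 8 mm | 0.62 | 7.4% | 4.7% | 4.7% |

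A separate simulation, with SD falling from 20 to 8 mm and correlation 0.8 per doubling of time, gave 7.6% (4,000 runs). Another under similar assumptions gave about 8.7%. When sphericity fails, the uncorrected interaction test therefore runs at about 7-9%. The overall group test does not move, because it uses one average per patient.

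**4. Baseline adjustment.** If baseline and postoperative VAS correlate at r, adjustment multiplies the residual variance by 1 - r^2. This is 0.99 at r = 0.1, 0.96 at 0.2, 0.91 at 0.3 and 0.75 at 0.5. The documents give no value of r.

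**The case against.** The strongest reply is that the plan is silent on these matters, not wrong.

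- **Dropping patients.** A reader might infer that the plan excludes anyone with a missed reading. It does not say so; exclusion is the default of the classical procedure. The miss rates are assumptions, and independence puts the loss near the top of its range. Follow-up is in PACU and on the ward at fixed times, so misses may be few. This stands, and the loss figures are conditional.
- **Sphericity.** A reader might infer that the method needs constant variance and constant correlation, or that the whole VAS comparison is invalid. Neither follows. Constant variance and correlation are sufficient for sphericity but not necessary. The overall group test stays at about 5%, and a Greenhouse-Geisser correction restores the interaction test to 4.3-4.8%. Sphericity alone would therefore not require a new method. The correction does nothing, however, for missed readings or for the lack of a committed estimate.
- **Baseline.** A reader might infer bias. Randomisation keeps the unadjusted comparison unbiased, so only precision is at stake. The gain could be slight if preoperative pain is near zero. That the baseline goes unused is itself read from silence, though the contrast with the QoR-15 entry supports it.
- **Estimates.** Section 8.2 does provide group summaries, and ANOVA does not rule out contrasts at each time. What is missing is a stated group difference with its interval.
- **Importance.** VAS is one of six unranked secondary items, and the documents do not call it the main pain outcome after opioid use.

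**Conclusion.** The concern holds in a limited form. Repeated measures ANOVA is the only VAS analysis named, and it comes with no sphericity correction, missing-data rule or use of the pre-block values. Its default form would exclude about 10-23% of patients at assumed independent miss rates of 2-5% per reading, and fewer if misses cluster. Its uncorrected group-by-time test would run at about 7-9% under the assumed non-spherical patterns. The documents do not support a claim that patients will certainly be lost, that the overall group comparison is inflated, or that the result is biased for want of baseline adjustment. The primary outcome and the sample size are not touched. This is a change that should be made, because a better method is available on data already collected, but the trial's main conclusion does not depend on it.

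**What to change.** Replace the VAS clause in Section 8.2. For rest and cough separately:

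- Fit a linear mixed model for repeated measures to all available readings at 1, 2, 4, 8 and 24 h. Include group, time (categorical), group-by-time and the pre-block VAS for the same state.
- Use an unstructured covariance and Kenward-Roger degrees of freedom.
- Report the group difference with 95% CI averaged over the five readings and at each time. Label the per-time differences as descriptive, since five times in two states give ten of them.
- State that patients with some missed readings stay in the model, and that this relies on readings being missing at random given the observed data.

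The cost is SAP wording and a little programming. The unstructured covariance needs 5 × 6 / 2 = 15 parameters from about 54-60 patients, which is why small-sample degrees of freedom are needed. The precision gained from baseline may be small. No extra data collection is required.
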